4.2 Descriptive Endpoints

4.2.1 All subjects

- Procedure-related death as adjudicated by a CEC.
- JETi-related AEs collected during JETi procedure, at discharge, and 30-day follow-up, as adjudicated by a CEC.
- Procedure-related access site complications such as hematoma, pseudoaneurysm (false aneurysm), perforation, as adjudicated by a CEC.
- **Treatment Used:** The number and percentage of patients having each of the following treatments:
 - JETi mechanical thrombectomy (MT) only
 - JETi in combination with one or more of the following treatments:

- **Short-Form Health Survey-12 (SF-12)** – score at baseline and 30-day visit.

4.2.2 Arterial and Arteriovenous Subjects

- Clot removal grade for each JETi-treated target vessel from pre-JETi angiogram to final angiogram (post-JETi thrombectomy and after any/all adjunctive therapies and prior to removal of the vascular sheath) per the grades in **Table 1**.
- Components of the MAE, up to 30 days post-JETi procedure, including device-related death, major amputation of treated limb, and major bleeding up to 30 days as adjudicated by a CEC.
- Ankle Brachial Index (ABI) of treated limb(s) at baseline and 30 days. Note this is applicable to lower extremity arterial subjects only.

- Rutherford classification of treated limb(s) at baseline and 30 days. Note this is applicable to lower extremity arterial subjects only.
- Re-thrombosis of JETi-treated vessel at 30-day follow-up, as assessed by investigator/physician reported.
- Patency as determined by duplex ultrasound at baseline and 30-day. Note that this endpoint will only apply to subjects treated for arteriovenous thrombus.
- **Vessel patency:** assessed by the independent imaging core laboratory using the Modified Thrombolysis in Myocardial Infarction (TIMI) classification called TIPI (Thrombo-aspiration in Peripheral Ischemia)⁵ (**Table 3**) for each JETi-treated vessel, assessed using angiogram
 - At post-JETi timepoint (post-JETi thrombectomy and prior to any adjunctive therapies to treat underlying culprit lesions)
 - At final timepoint (post-JETi thrombectomy and after any/all adjunctive therapies and prior to removal of the vascular sheath)

If no adjunctive therapies or devices are used after JETi, post-JETi TIPI score is also final TIPI score.

Table 3. Thrombo-aspiration in Peripheral Ischemia (TIPI)

Description	TIPI score
No recanalization of the thrombotic occlusion	0
Incomplete or partial recanalization of the thrombotic occlusion with no distal flow	1
Incomplete or partial recanalization of the thrombotic occlusion with any distal flow	2
Complete recanalization of the thrombotic occlusion with normal distal flow	3

- Acute success, as per [REDACTED] (**Table 3**):
 - Device success: Near complete or complete recanalization of occluded vessel, defined as post-JETi [REDACTED]
 - Technical success: Near complete or complete recanalization of occluded vessel, defined as final [REDACTED] where [REDACTED] evaluation occurs after JETi system and any other adjunctive device or procedures.
 - Procedural success: Technical success with no JETi-related MAEs within 5 days of registration or by discharge, whichever occurs first

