The JETi Hong Kong PMS is a single-arm, multi-center study registering approximately 20 subjects from up to 5 sites in Hong Kong. Both prospective and retrospective consent (if all assessments needed for primary endpoints are complete) are permitted. In cases of prospective consent, subject participation will be up to 30 days. If consent occurs after the procedure, duration of participation may vary given timing of consent but will not exceed 30 days.

This study will collect data on how the JETi System performs in the treatment of patients undergoing a percutaneous thrombectomy procedure for peripheral thrombosis. Subjects treated for arterial, venous, or arteriovenous thromboses, and subject with diagnoses such as acute limb ischemia (ALI), chronic limb ischemia/chronic limb threatening ischemia (CLI/CTLI), peripheral artery disease (PAD), deep vein thrombosis (DVT), hemodialysis access thrombosis, and others may be included. The details of data to

¹ Cournoyer-Rodrigue J, Bui TB, Gilbert P, et al. Percutaneous Thrombectomy with the JETi8 Peripheral Thrombectomy System for the Treatment of Deep Vein Thrombosis. *J Vasc Interv Radiol.* 2020;31(3):444-453.e2. doi:10.1016/j.jvir.2019.10.022

² Khalsa B., Luu K., Gilbert B., et al. Single-session treatment of lower extremity venous thrombosis using a novel thrombectomy device: results of a pilot study. *J Vasc Interv Radiol.* 2020; 31(3):S83. doi:10.1016/j.jvir.2019.12.217

³ Razavi C, Khalsa B, Openshaw L, Razavi MK. Single-Session Treatment of Patients with Symptomatic Iliocaval and Iliofemoral Deep Vein Thrombosis: Technical Results of a Prospective Pilot Study. *J Vasc Interv Radiol.* 2022;33(2):183-188. doi:10.1016/j.jvir.2021.10.011

⁴ Dandu C, Natour A, Onofrey K, et al. Single-Center Experience with JETi Aspiration Thrombectomy for Acute and Subacute Lower Limb Ischemia. Presented at the Vascular Annual Meeting (VAM), June 2022.

be collected and the timepoints for the purpose of this study are described in this plan. Each participating investigator will determine and implement the best treatment strategy for their patients based on the clinical situation and local physician practices. This study will be conducted in accordance with this CIP. All investigators involved in the conduct of the study will be qualified by education, training, and experience to perform their tasks and this training will be documented appropriately.

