4.1 Primary Endpoints

4.1.1 Arterial and Arteriovenous Subjects

For subjects treated for arterial thrombosis (may include diagnoses such as acute limb ischemia, chronic limb ischemia/chronic limb threatening ischemia, peripheral artery disease, etc.) or arteriovenous (AV graft, AV fistula) thrombosis, all endpoints are descriptive.

For subjects treated for arterial or arteriovenous thrombosis, the primary endpoints are:

- **Clot removal grade** for each JETi-treated target vessel from pre-JETi angiogram to post-JETi angiogram (post-JETi thrombectomy and prior to any adjunctive therapies to treat underlying culprit lesions) per the grades in **Table 1** (vessel basis). The independent imaging core laboratory will be responsible for assessing this endpoint.
- **Composite of JETi-related major adverse events** (MAEs) up to 30 days post-JETi procedure, defined as the following JETi-related events adjudicated by a clinical events committee (CEC) (subject basis) death, major amputation of the treated limb, or major bleeding. Refer to **Appendix II** for definitions of major adverse events.

Table 1. Clot Removal Grade

Grade I	< 50% reduction
Grade II	50- <95% reduction
Grade III	95 - 100% reduction

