5.3.2 Inclusion Criteria

5.3.2.1 General Inclusion Criteria

1. Subject was treated or is expected to be treated for acute/subacute thrombosis, as determined by investigator, in the peripheral vasculature with the JETi Hydrodynamic Thrombectomy System.
2. Subject or legally authorized representative must provide written informed consent
3. Subject must be ≥ 18 years of age and of Asian race.

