6.1 Arterial and Arteriovenous Subjects

At Baseline, demographic information, medications, clinical assessment, physical exam and a medical history will be collected. Laboratory assessments, up to 14 days prior to the procedure, will be recorded and may include estimated glomerular filtration rate (eGFR), serum creatinine (SCr), blood urea nitrogen (BUN), potassium (K), hemoglobin (Hgb), platelets (plt), prothrombin time (PT), international normalized ratio (INR) and activated partial thromboplastin time (aPTT).

The pre-JETi angiogram will be used to assess the initial degree of clot burden after catheter insertion into the vessel and prior to JETi Thrombectomy. The post-JETi Thrombectomy angiogram will be used to assess clot removal after JETi Thrombectomy and prior to any adjunctive therapies used to treat underlying culprit lesions. The final angiogram will be completed to assess clot removal after JETi Thrombectomy and any/all adjunctive therapies and prior to removal of the vascular sheath. All treated

vessels will be assessed using the provided clot removal grades (**Table 1**). All angiograms are requested to be transmitted to the core lab for analysis. Guidance from the imaging core laboratory will be provided for reference.

DUS will be collected at baseline and 30-Day Follow-Up for subjects with arteriovenous thrombosis. Refer to the DUS core laboratory guidelines for detailed information. All DUS completed are requested to be transmitted to the core lab for analysis.

An ABI examination is required at Baseline and 30 Days. Rutherford classification is required at Baseline and 30 Days. Note: baseline ABI (within 3 months prior to procedure) and Rutherford assessment (within 4 days prior to procedure) can be obtained via a non-study physician, including a referring physician; this will not be considered a protocol deviation. Note these are applicable to lower extremity arterial subjects only.

The Short Form (SF)-12 is a self-reported outcome quality of life measure. Its completion is requested at Baseline and at 30 days. For post-procedurally consented subjects, a baseline SF-12 will not be collected as the validity of this assessment is not supported when collected retrospectively.

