6.1.6 Schedule of Events

The schedule of assessments for Arterial Subjects is listed in **Table 4**.

Table 5. Assessment Schedule for Arterial and Arteriovenous Subjects

CIP Activity	Baseline	Index Procedure	Discharge	30 Days Follow-up ¹ (± 7 days)	Unscheduled Visit
Enrollment ²	X				
Demographics	X				
Medical history	X				
Medications	X	X	X	X	X ³
Laboratory assessments					
eGFR	X ⁴				
Serum Creatinine (SCr)	X ⁴				
Blood Urea Nitrogen (BUN)	X ⁴				
Potassium (K)	X ⁴				
Hemoglobin (Hgb)	X ⁴				
Platelets (Plt)	X ⁴				
International Normalized Ratio (INR)	X ⁴				
Prothrombin Time (PT)	X ⁴				
Activated Partial Thromboplastin Time (aPTT)	X ⁴				
Clinical assessment	X ⁴				
Physical exam	X ⁴				
ABI	X ^{5, 6}			X ⁶	
Rutherford classification	X ^{6, 7}			X ⁶	
Imaging assessment – Angiogram		X ⁸			
Imaging assessment – DUS	X ⁹			X ⁹	
QOL (SF-12)	X ¹⁰			X	
Adverse event assessment/Device Deficiency assessment		X ¹¹	X ¹¹	X ¹¹	X ¹¹
Procedure, treatment information		X			

¹ in-office visit is required at 30-day follow-up. A telephone contact or virtual visit is an option only for subject who would otherwise miss the visit due to being unable to complete an office visit

² retrospective consent is permitted

³ unscheduled medications reported in Adverse Event form when applicable

⁴ assessment done within 14 days prior to procedure is acceptable

⁵ ABI done within 3 months prior to procedure is acceptable. In emergent ALI cases, missing ABI at baseline will not be considered a protocol deviation

⁶ can be obtained via a non-study physician, including a referring physician; this will not be considered a protocol deviation

⁷ Rutherford classification done within 4 days prior to JETi procedure is acceptable

⁸ includes pre-JETi, post-JETi, and final (after JETi and all adjunctive device/treatment) angiograms

⁹ only applicable for arteriovenous thrombosis

¹⁰ not applicable for post-procedure consented subjects

¹¹ Serious adverse events (SAEs) and device deficiencies must be reported within 3 calendar days of Site becoming aware

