8.8 Procedures for Accounting for Missing Data

Analysis will be based on available data with missing data excluded. Any unused or spurious data will be noted as appropriate in the final report.

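### Under the available-data rule, subjects who die and probably limbs lost to amputation drop out of the 30-day Rutherford summary, so any such event makes that summary look better than the cohort's result

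*Combined protocol and SAP*

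**What the plan says.** Section 4.2.2 lists among the descriptive endpoints "Rutherford classification of treated limb(s) at baseline and 30 days". Section 6.1 makes the assessment mandatory ("Rutherford classification is required at Baseline and 30 Days") and limits it, together with the ankle brachial index, by diagnosis: "Note these are applicable to lower extremity arterial subjects only". The 30-day visit has a window of plus or minus 7 days (6.1.4).

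Section 8.2 summarises categorical variables by counts and percentages. It specifies no paired table, change score or responder definition for Rutherford class. Section 8.1 puts every registered subject in the analysis. Section 8.8 says: "Analysis will be based on available data with missing data excluded". No visible text says how a treated limb amputated before the 30-day visit, or a subject who has died by then, enters the 30-day Rutherford summary.

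Death and limb loss are reported elsewhere:
- Major amputation of the treated limb and death are parts of the primary safety composite (4.1.1) and are listed again as its components (4.2.2). The composite is restricted to JETi-related events.
- Procedure-related death is an endpoint for all subjects (4.2.1). Appendix II treats a death within 30 days as procedure related unless the history or autopsy shows otherwise.
- All serious adverse events are collected through the 30-day visit (7.3.1).

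**The concern.** Clinical benefit is part of the study objective (2.1). Rutherford class and the ankle brachial index are the two clinical limb-status measures taken at both baseline and 30 days in these subjects. The schedule in 6.1.6 tolerates a missing baseline ankle brachial index in emergent acute limb ischemia, so for some subjects Rutherford class may be the only such measure at both times.

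Death and loss of the treated limb are the worst results a limb-status measure can have, and they are not missing at random. A rule that handles them like a skipped visit removes the poorest results from the later column and leaves the same limbs in the earlier one. A reader who sets the two columns side by side would take part of that shift for improvement. The group is a fraction of about 20 subjects shared among arterial, arteriovenous and venous disease, so one limb can move a percentage noticeably.

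**Working it through.** **No figure to reproduce.** The plan states no Rutherford result or target, no number of lower extremity arterial subjects and no visible expected rate of death or amputation. Every count below is an assumption, with one treated limb per subject.

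**Step 1: how the rules combine.** Baseline class is recorded before the procedure, so in principle all *n* treated limbs contribute. At 30 days, 8.8 keeps only limbs with a recorded class. If *k* limbs have no class because of death or amputation, the 30-day denominator is *n* − *k*. For death this follows directly. For amputation it is the probable reading, since the plan is silent.

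**Step 2: effect on the class distribution, the statistic the plan does report.** Take *n* = 8 and *k* = 2, and suppose both lost limbs were in the worst class present at baseline and no other limb was in that class. Baseline share in that class: 2/8 = 25%. Thirty-day share: 0/6 = 0%. The column improves by 25 points although no surviving limb has changed class. This is an extreme allocation, chosen to show the mechanism.

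**Step 3: effect on a percentage improved.** The plan defines no such measure; it is used here only for size. With *x* limbs improved:
- available-data percentage = *x*/(*n* − *k*)
- percentage of all treated limbs = *x*/*n*
- difference = [*x*/(*n* − *k*)] × (*k*/*n*)

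| n | k | x | Available data | All treated limbs | Difference (points) |
|---|---|---|---|---|---|
| 8 | 2 | 5 | 5/6 = 83.3% | 5/8 = 62.5% | 20.8 |
| 5 | 1 | 3 | 3/4 = 75.0% | 3/5 = 60.0% | 15.0 |
| 10 | 2 | 6 | 6/8 = 75.0% | 6/10 = 60.0% | 15.0 |
| 20 | 1 | 15 | 15/19 = 78.9% | 15/20 = 75.0% | 3.9 |
| any | 0 | any | x/n | x/n | 0 |

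With roughly 60% to 100% of assessable limbs improved, one event gives about 3 points (*n* = 20) to 20 points (*n* = 5). Two events give about 6 points (*n* = 20) to 20 points (*n* = 10).

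For scale, the exact 95% intervals in the *n* = 10 row are 34.9% to 96.8% for 6/8 and 26.2% to 87.8% for 6/10. The shift is well inside sampling uncertainty, but it always goes the same way.

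**Step 4: chance that the issue arises.** If each of 10 subjects has probability *r* of death or amputation by day 30, the chance of at least one event is 1 − (1 − *r*)^10. This gives 18%, 40%, 65% and 89% for *r* = 2%, 5%, 10% and 20%. These rates are assumed.

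**The case against.** The best defence is that the bad outcomes are not hidden. Amputation and death sit in the primary safety composite, procedure-related death is reported with a default that favours attribution, and all serious adverse events are collected. A redacted list in 7.3.1 covers further events collected regardless of relatedness and may include amputation. The endpoint is also descriptive and untested, and the plan never promises a change score or a percentage improved. If nobody dies or loses a limb, nothing goes wrong.

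Much of this stands, and it limits the point to a reporting improvement. It does not remove it. The amputation component counts only JETi-related events, so a treated limb lost for another reason is assured a place only among the serious adverse events. None of the separate reporting puts the lost limbs back into the limb-status table, where baseline and 30-day percentages will be read against each other.

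Three stronger readings might be inferred, and the documents do not support them:
- **That the Rutherford result is biased upward as a matter of fact.** The bias is zero unless such an event occurs, and no rates are given.
- **That the endpoint cannot show limb benefit.** This is too strong for an untested descriptive measure. The single-arm design limits any claim of benefit however the table is built.
- **That acute and chronic Rutherford grades are mixed in one table.** The arterial group "may include diagnoses such as acute limb ischemia, chronic limb ischemia/chronic limb threatening ischemia, peripheral artery disease, etc", subject to the entry rule on acute or subacute thrombosis. But the visible text gives no Rutherford categories, does not say that different categories apply by presentation, and does not say that presentations share a table. Sections 8.5 and 8.6 show no text, 8.7 is partly redacted, and the case report forms are under separate cover. What remains is an undefined scale, which is a matter for clarification.

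**Conclusion.** The point holds in conditional form. As written, 8.8 takes a subject who dies before the 30-day visit, and probably an amputated limb, out of the 30-day Rutherford summary, while the same limb stays in the baseline summary. If any such event occurs, the 30-day distribution looks better than it would over all treated limbs, and the two columns rest on different limbs. If none occurs, there is no bias.

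On the assumed counts, one or two events in groups of 5 to 20 limbs move a percentage improved by anything from about 3 points to more than 20. That size depends on the assumed group size, event count and share improved, and on an improvement measure the plan does not define. The direction depends only on death and limb loss being counted as poor outcomes. This is a worthwhile, inexpensive improvement to a secondary descriptive endpoint and does not affect the primary endpoints.

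**What to change.** In 4.2.2 and 8.8:
- Present Rutherford class as a paired baseline-to-30-day table with all treated lower extremity arterial limbs as the denominator.
- Add explicit 30-day rows for major amputation of the treated limb from any cause (Appendix II definition) and for death. Count each limb once, with the order of precedence stated.
- Show truly missing assessments (for example, subjects lost to follow-up or seen only by telephone) in their own row, and do not merge them with the two rows above.
- State whether these events are counted to day 30 or to the visit, since the window runs to day 37 (30 + 7).

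No new assessment should be needed, because deaths and major amputations should already be captured as serious adverse events. The cost is two or three table rows and, if events occur, a slightly less favourable 30-day figure.

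As a secondary clarification only, name the Rutherford categories used at each visit. If acute and chronic presentations use different categories, tabulate them separately. That would make already small groups smaller.

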4.2.3 Venous Subjects

- Percent of treated vessels (in lower extremity DVT) with $\geq 75\%$ thrombus reduction from pre-JETi venogram to post-JETi venogram (post-JETi thrombectomy and before any adjunctive therapies to treat underlying culprit lesions) via modified Marder score. The independent imaging core laboratory will be responsible for assessing this endpoint. Note this is applicable to lower

⁵ de Donato G, Pasqui E, Sponza M, et al. Safety and Efficacy of Vacuum Assisted Thrombo-Aspiration in Patients with Acute Lower Limb Ischaemia: The INDIAN Trial. *Eur J Vasc Endovasc Surg.* 2021;61(5):820-828. doi:10.1016/j.ejvs.2021.01.004

extremity DVT subjects only. The effectiveness outcome for subjects treated for venous thrombosis that is not lower extremity DVT as defined in Appendix II (e.g., upper extremity DVT) will be assessed by clot removal grade, as defined in Section 4.1.1.

- Components of the MAE up to 30 days post-JETi procedure, including the following JETi-related events adjudicated by a CEC: device-related death, symptomatic pulmonary embolism (PE), major bleeding, and re-thrombosis of JETi treated vessel(s).
- The Villalta Post Thrombotic Syndrome (PTS) severity scale at baseline, and 30-day follow-up. Note this is applicable to lower extremity DVT subjects only.
 - Edema component score from the Villalta Post Thrombotic Syndrome (PTS) severity scale at baseline, and 30-day follow-up.
- A 7-point Likert Scale for leg pain at baseline, discharge, and 30-day follow-up. Note this is applicable to lower extremity DVT subjects only.
- Venous patency and compressibility as determined by duplex ultrasound at baseline, and 30-day follow-up. The independent imaging core laboratory will be responsible for assessing this endpoint.
- Acute success, [REDACTED], assessed by core laboratory:

- Device success: post-JETi thrombus removal grade II-III [REDACTED]
 - Technical success: Final thrombus removal grade II-III, [REDACTED] where final [REDACTED] evaluation occurs after JETi system and any other adjunctive device or procedures.
- Procedural success: Technical success with no JETi-related MAEs within 5 days of registration or by discharge, whichever occurs first.

If no adjunctive therapies or devices are used after JETi, post-JETi [REDACTED] score is also final [REDACTED] score.

[REDACTED]		[REDACTED]		[REDACTED]	

5 SUBJECT SELECTION AND WITHDRAWAL

5.1 Subject Population

This study will register subjects of all genders from the patient population undergoing percutaneous treatment of thrombosis in the peripheral vascular system.

5.2 Subject Recruitment/Screening and Informed Consent

5.2.1 Subject Recruitment and Screening

A member of the site's study team previously trained to the CIP should evaluate patients for general study eligibility criteria. A patient who does not satisfy all general eligibility criteria prior to informed consent is considered a recruitment failure and should not be enrolled in the study.

Sites will ask patients meeting general inclusion criteria and no general exclusion criteria to sign an Informed Consent Form (ICF) following the established Informed Consent process (described in **Section 5.2.2**) if they wish to participate in the study.

Enrolled (consented) subjects who do not have a JETi Catheter introduced into the intended vasculature are considered a screen failure and should be withdrawn from the study. The Principal Investigator or the delegated study personnel will record the screen failure in the hospital records and on a recruitment/screening log as required.

